1. INTRODUCTION

Cutaneous squamous cell carcinoma (cSCC) is a common malignancy in patients receiving immunosuppressive therapy, including solid organ transplant recipients (SOTRs). These patients have an estimated 60- to 250-fold increased risk of cSCC development and are particularly vulnerable to the development of highly aggressive or catastrophic cSCC [1-4]. Post-transplant cSCC occurs at a younger age and is more aggressive than in non-transplant cohorts, with 30% recurring within 1 year and up to 8% of disease associated with metastasis [5]. The median survival after diagnosis of metastasis is 3 years [6]. Cemiplimab, an anti-PD1 antibody, recently became the first agent to achieve FDA approval for the treatment of advanced cSCC [7, 12]. However, due to the risk of graft rejection, the role of checkpoint blockade in the SOTR population is extremely limited. In retrospective series, the rate of graft rejection has ranged between 37-41% with a significant percentage of these patients dying as a result [8]. There is a dearth of data to guide decision making in patients who cannot receive cemiplimab. Two small phase II studies investigating epidermal growth factor receptor (EGFR) antagonists have demonstrated response rates of 28 and 31%, however it is unclear if these agents have any survival benefit and it is unknown if these response rates are seen in SOTR [13, 14]. Thus, there remains a large unmet medical need for novel strategies in these patients.

The Janus kinase-signal transducer and activator of transcription (JAK-STAT) pathway plays a critical role in tumorigenesis and has been implicated in cSCC. STAT proteins regulate the transcription of genes involved in cytokine signaling, cell proliferation, and tumorigenesis [9]. Elevated levels of STAT3 have been observed in a number of human epithelial cancers [10, 11]. Pre-clinical data from our group supports the role of JAK1/2 co-inhibition as a potential therapeutic strategy in cSCC. We propose to evaluate the efficacy of ruxolitinib, an orally administered inhibitor of JAK1/2, in solid organ transplant recipients with advanced cSCC. Paired pre-treatment and on-treatment biopsies will also be obtained to further define the mechanism of response and resistance to JAK1/2 inhibition in this population.

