2. STUDY OBJECTIVES

2.1 Primary Objective

- To determine the efficacy of ruxolitinib in post-transplant patients with advanced cutaneous squamous cell carcinoma as determined by overall response rate.

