6. SUBJECT SELECTION AND WITHDRAWAL

6.1 Inclusion Criteria

1. Histologically confirmed diagnosis of cSCC.
2. Unresectable or metastatic cSCC.
3. History of solid-organ transplant requiring immunosuppression
4. Allowable prior therapies:
 - a. A maximum of 4 prior therapies for metastatic disease are allowed.
5. Male or female subjects, age 18 years or older.
6. ECOG performance status ≤ 2 (Appendix A)
7. Life expectancy of ≥ 3 months.
8. Laboratory parameters within the following Protocol-defined range. All screening laboratory tests should be performed within 28 days of treatment initiation and must be independent of hematopoietic growth factor support.
 - Absolute neutrophil count $\geq 1.5 \times 10^9/L$.
 - Platelets $\geq 100 \times 10^9/L$.
 - Hemoglobin $\geq 9 \text{ g/dL}$ (transfusion is acceptable to meet this criteria)
 - Serum creatinine $\leq 1.5 \times$ institutional upper limit of normal (ULN) OR calculated creatinine clearance $\geq 50 \text{ mL/min}$ for subjects with creatinine levels $> 1.5 \times$ institutional ULN.
 - Aspartate aminotransferase, alanine aminotransferase, alkaline phosphatase $\leq 2.5 \times$ ULN, or $\leq 5 \times$ ULN in subjects with liver metastases.
 - Total bilirubin $\leq 1.5 \times$ ULN
 - **Note:** patients with hyperbilirubinemia clinically consistent with an inherited

disorder of bilirubin metabolism (eg, Gilbert syndrome) will be eligible at the discretion of the principal investigator.

- International normalized ratio (INR) or prothrombin time (PT) $< 1.5 \times$ ULN unless subject is receiving anticoagulation therapy as long as PT or INR is within therapeutic range of intended use of anticoagulant.
- Activated partial thromboplastin time (aPTT) $< 1.5 \times$ ULN unless subject is receiving anticoagulant therapy, as long as PTT is within therapeutic range of intended use of anticoagulants.

9. Presence of baseline measureable disease by RECIST v1.1 for solid tumors, defined as at least one lesion that can be accurately measured in at least one dimension (longest diameter to be recorded for non-nodal lesions and short axis for nodal lesions) as ≥ 20 mm with conventional techniques or as ≥ 10 mm with spiral CT scan, MRI, or calipers by clinical exam. (See Section 15.4 for the evaluation of measurable disease).

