6.2 Exclusion Criteria

1. At least 21 days must have elapsed since the last dose of systemic chemotherapy or immunotherapy and the first dose of study drug.
2. At least 14 days must have elapsed since the last dose of radiation therapy and the first dose of study drug.
3. Patients who have previously been treated with a JAK inhibitor.

4. Patients who are receiving any other investigational agents concurrently.
5. Patients who have had recent major surgery within a minimum 4 weeks prior to starting study treatment, with the exception of surgical placement for vascular access.
7. Patients with a history of allergic reactions attributed to compounds of similar chemical or biologic composition to ruxolitinib.
8. Patients with symptomatic or growing brain metastases. Patients with brain metastases that have been treated and have remained stable for at least one month prior to initiation of study therapy are eligible.
9. Concurrent use of strong CYP3A4 or CYP3A4 substrate drugs with a narrow therapeutic range within 14 days or 5 drug half-lives, whichever is longer, before start of study drug. A list of strong CYP3A4 and 2C8 inhibitors and inducers can be found in Appendix C.
10. HIV-positive patients on combination antiretroviral therapy are ineligible because of the potential for pharmacokinetic interactions with ruxolitinib. In addition, these patients are at increased risk of lethal infections when treated with marrow-suppressive therapy.
11. Subjects with known active hepatitis B or C, or chronic hepatitis B or C requiring treatment with antiviral therapy.
12. Uncontrolled intercurrent illness including, but not limited to, ongoing or active infection, symptomatic congestive heart failure, unstable angina pectoris, cardiac arrhythmia, or psychiatric illness/social situations that would limit compliance with study requirements.
13. Patients being actively treated for a second malignancy.

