When ruxolitinib is administered with strong CYP3A4 inhibitors (such as, but not limited to, boceprevir, clarithromycin, indinavir, itraconazole, ketoconazole, lopinavir/ritonavir, ritonavir, mibefradil, nefazodone, nefazodone, nelfinavir, posaconazole, saquinavir, telaprevir, telithromycin, voriconazole) as well as fluconazole (a dual inhibitor of CYP3A4 and CYP2C9, see also Section 5.1.5.4), the dose should be reduced to approximately 50% of the dose rounding to the nearest dosage strength. The concomitant use of ruxolitinib with fluconazole doses of greater than 200 mg daily should be avoided. More frequent monitoring of hematology parameters and clinical signs and symptoms of ruxolitinib related adverse reactions is recommended upon initiation of a strong CYP3A4 inhibitor. No dose adjustment is necessary when a mild or moderate CYP3A4 inhibitor is used concomitantly with ruxolitinib. No dose adjustment is necessary when a CYP3A4 inducer (such as, but not limited to, avasimibe, carbamazepine, phenobarbital, phenytoin, rifabutin, rifampin, rifampicin, St. John's) is used concomitantly with ruxolitinib. No dose adjustment is necessary when ruxolitinib is administered with a CYP3A4 substrate. Patients should be closely monitored and the ruxolitinib dose titrated based on safety and efficacy.

Women of child-bearing potential

Women of child-bearing potential must take appropriate precautions to avoid pregnancy during treatment. In case pregnancy occurs, risk-benefit evaluations must be carried out on an individual basis with careful counseling regarding potential risk to the fetus using the most recent data available.

Embryo-fetal development studies with ruxolitinib in rats and rabbits did not indicate teratogenicity. Ruxolitinib was embryotoxic and fetotoxic in rats (increases in post-implantation loss and reduced fetal weights). The potential risk for humans is unknown.

Breast-feeding

Women taking ruxolitinib should not breast-feed.

Overdosage

There is no known antidote for overdoses with ruxolitinib. Single doses up to 200 mg have been given with acceptable acute tolerability. Higher than recommended repeat doses are associated with increased myelosuppression including leukopenia, anemia and thrombocytopenia.

Appropriate supportive treatment should be given. Hemodialysis is not expected to enhance the elimination of ruxolitinib.

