12. STUDY EVALUATIONS

12.1 Screening Phase

The screening phase will be up to 28 days. Screening is the interval between the signing of the informed consent form (ICF) and the day the subject receives the first dose of treatment in the study (Cycle 1 Day 1). Informed consent must be obtained before performing any study-specific procedures not considered standard of care. Assessments that are required to demonstrate eligibility may be performed over the course of 1 or more days during this phase.

Results from the screening visit evaluations will be reviewed to confirm subject eligibility before enrollment or the administration of study drug. Tests with results that fail eligibility requirements may be repeated during the screening phase if the investigator believes the results to be in error. Additionally, a subject who fails screening may repeat the screening process 1 time if the investigator believes there has been a change in eligibility status (eg, after recovery from an infection).

See **Section 13** for detailed list of screening procedures.

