23.3 Appendix C: Strong CYP3A4 and 2C8 Inhibitors and Inducers

| Strong Inhibitors | Strong Inducers |
|--|--|
| Protease Inhibitors: 
• Ritonavir• Indinavir• Nelfinavir | Anticonvulsants, mood stabilizers: 
• Phenytoin• Carbamazepine• Oxcarbazepine |
| Macrolide antibiotics: 
• Erythromycin• Telithromycin• Clarithromycin | Non-nucleoside reverse transcriptase inhibitors: 
• Efavirenz• Nevirapine• Etravirine |
| Azole antifungals: 
• Fluconazole• Ketoconazole• Itraconazole | Others: 
• Phenobarbital• Rifampicin• Modafinil• Hyperforin (constituent of St Johns Wort)• Cyproterone (antiandrogen, progestin) |
| Others: 
• Chloramphenicol• Nefazodone• Bergamottin (constituent of grapefruit juice)• Aprepitant• Verapamil• Gemfibrozil• Trimethoprim | |

Columbia University Medical Center
Herbert Irving Comprehensive Cancer Center
Version Date: 27 Jul 2023

| | |
|---|--|
| 
• Thiazolidinedione• Montelukast• Quercetin | |
|---|--|

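### Exclusion 9 bars narrow-therapeutic-range CYP3A4 substrates and does not exempt the anti-rejection drugs of a trial that enrols only transplant recipients

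*Combined protocol and SAP*

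**What the plan says.** Section 2.1 sets the primary objective: "To determine the efficacy of ruxolitinib in post-transplant patients with advanced cutaneous squamous cell carcinoma as determined by overall response rate". Section 6.1, item 3 limits entry to patients with a "History of solid-organ transplant requiring immunosuppression".

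Section 6.2, item 9 then excludes "Concurrent use of strong CYP3A4 or CYP3A4 substrate drugs with a narrow therapeutic range within 14 days or 5 drug half-lives" (the longer of the two), counted back from the start of study drug. It refers the reader to "Appendix C: Strong CYP3A4 and 2C8 Inhibitors and Inducers" (section 23.3). That appendix names inhibitors and inducers only. It lists no substrates and no exempt drugs.

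Three other places bear on the point:

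- Section 8.2 requires all concurrent drugs to be recorded and the principal investigator to be told of agents that may affect CYP3A4.
- Section 10.1 says "No dose adjustment is necessary when ruxolitinib is administered with a CYP3A4 substrate".
- Section 21.6 says that eligibility deviations will not be approved.

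**The concern.** Every patient in this trial has a transplant that needs immunosuppression. If the usual anti-rejection drugs belong to the class that item 9 bars, the criterion removes much of the population that the trial was set up to study. A site has three ways to respond, and each does harm.

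- **Screen-fail the patient.** Those who enter are selected by immunosuppressive regimen. The response rate then does not describe the post-transplant population of section 2.1, and accrual slows.
- **Stop the drug.** The graft is put at risk. The protocol itself gives rejection as the reason another treatment is little used here: "due to the risk of graft rejection, the role of checkpoint blockade in the SOTR population is extremely limited". No section instructs, permits or plans for such a washout.
- **Ignore the criterion.** The patient is then ineligible on the record. Section 17.5.2 bases its conclusions on eligible patients, while section 17.2 counts everyone who is dosed, so the primary denominator becomes open to dispute.

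**Working it through.** **1. Is there an exemption?** Sections 6.1, 6.2, 8.2, 10.1 and 23.3 were read for one.

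| Place | What it does | Exempts immunosuppressants? |
|---|---|---|
| 6.1, item 3 | Requires a transplant needing immunosuppression | No |
| 6.2, item 9 | Bars narrow-range CYP3A4 substrates in the window | No |
| 8.2 | Record all drugs, alert the principal investigator | No |
| 10.1 | Ruxolitinib dosing advice with substrates | No; does not set eligibility |
| 23.3 | Lists inhibitors and inducers | No |

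Section 16.3 mentions eligibility waivers, which conflicts with section 21.6. A case-by-case waiver would not be an exemption in any event.

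**2. How long is the drug-free window?** Window = max(14 days, 5 × half-life). Five half-lives exceed 14 days when the half-life is above 14/5 = 2.8 days = 67.2 h. Section 12.1 states: "The screening phase will be up to 28 days". The shortest possible window is therefore 14/28 = 50% of the longest possible screening phase.

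**3. What could it do to accrual?** Inputs: 35 patients and 1 patient per site every 2 months (section 17.3); 3 sites, last patient at about 24 months and a study duration of 36 months (Synopsis).

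The plan's own figure first: 35 / (3 × 0.5 per month) = 35 / 1.5 = 23.3 months, which agrees with about 24.

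Now let *f* be the share of otherwise eligible candidates who take a barred substrate. The documents give no value, so *f* is an assumption, shown over a range. The site rate is taken to apply before item 9 removes anyone.

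Accrual time = 23.3 / (1 − *f*). Expected enrolment in 24 months = 24 × 1.5 × (1 − *f*) = 36 × (1 − *f*).

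| *f* (assumed) | Months to enrol 35 | Enrolled in 24 months |
|---|---|---|
| 0% | 23.3 | 36.0 |
| 25% | 31.1 | 27.0 |
| 50% | 46.7 | 18.0 |
| 80% | 116.7 | 7.2 |
| 90% | 233.3 | 3.6 |

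Accrual alone reaches 36 months when *f* = 1 − 35/(1.5 × 36) = 1 − 35/54 = 35%.

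**The case against.** The strongest reply is that the decisive step lies outside the documents. They do not say which immunosuppressants recipients take, and they class none as a narrow-range CYP3A4 substrate. Cyclosporine appears only in the title of a cited study. Without the pharmacology premise there is no conflict. This is true, and it is why the premise is labelled an assumption and the excluded share is left open. It also makes the conflict practical and not logical: a recipient on agents outside the class can meet both criteria.

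A second reply is that item 9 is a drafting slip. A noun is missing after the first mention of CYP3A4, its only list covers inhibitors and inducers, and section 10.1 contemplates giving ruxolitinib with a substrate. A bar on the trial's own population is unlikely to have been intended. That may well be so, but the substrate clause is complete and explicit. Eligibility is checked centrally against source documents, including medication lists (section 7.1), so sites cannot safely read the clause away.

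Third, a washout is speculative, since the direct result of an exclusion is a screen failure, and the rejection figures in section 1 concern checkpoint blockade. Nothing in the documents shows that response differs by regimen. These points stand. The graft risk arises only if someone stops the drug in order to qualify, and the effect on the estimate is a loss of representativeness whose direction is unknown. The Simon boundaries and the null rate are unaffected.

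**Conclusion.** The concern holds, and item 9 must be fixed. The documents alone establish the bar, the window of at least 14 days, the absence of an exemption, and a population made up entirely of recipients who need immunosuppression. One premise comes from general pharmacology: that calcineurin and mTOR inhibitors are narrow-range CYP3A4 substrates. On that premise, the criterion as written either screens out recipients maintained on these drugs or presses them to stop anti-rejection treatment.

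The excluded share cannot be derived from the documents, though it is potentially large. The accrual figures show what follows from assumed shares and do not estimate the true one. Confidence is medium because of the outside premise.

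**What to change.** Replace item 9 with text to this effect:

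> Use of a strong CYP3A4 inhibitor or inducer (Appendix C), or of a narrow-therapeutic-range CYP3A4 substrate that is not a maintenance transplant immunosuppressant, in the 14 days or 5 half-lives (the longer period applies) preceding the first dose. Maintenance transplant immunosuppressants are allowed, with drug levels monitored according to local practice.

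Update the eligibility checklist to match. If the sponsor does mean to exclude recipients on these drugs, it should say so and restate the population in section 2.1.

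The cost is an amendment to one criterion and to the checklist, with no added visits or patients. The downside is that patients on interacting immunosuppressants will enter. Neither study calendar (sections 13.1 and 13.2) lists immunosuppressant levels, so their safety will depend on monitoring by local practice.

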6.3 Inclusion of Women and Minorities

Both men and women of all races and ethnic groups are eligible for this trial.

6.4 Subject Recruitment

A member of the patient's treatment team, the protocol investigator, or research team at the multi-center sites will identify potential research participants. If the investigator is a part of the treatment team, s/he will screen the patient as to eligibility, and will discuss the study and the possibility of enrollment in the research study with the patient. The preliminary screen of eligibility will be confirmation for the diagnosis of advanced cutaneous squamous cell carcinoma.

Potential subjects that meet these basic criteria will be referred by their treatment physician to the investigator, co-investigators, or research staff of the study. Minority and women are well represented in cutaneous oncology clinics, and we expect that they will be well represented in the trial accrual. The principal investigator, [name], will be available to all patients for further questions and information through a contact number will be provided on the consent form.

During the initial conversation between the investigator/research staff and the patient, the patient

may be asked to provide certain health information that is necessary to the recruitment and enrollment process. The investigator/research staff may also review portions of their medical records in order to further assess eligibility. They will use the information provided by the patient and/or medical record to confirm that the patient is eligible and to contact the patient regarding study enrollment. If the patient turns out to be ineligible for the research study, the research staff will destroy all information collected on the patients during the initial conversation and medical records review, except for any information that must be maintained for screening log purposes.

6.5 Early Withdrawal of Subjects

When and How to Withdraw Subjects

Patients may withdraw from study at any time. Patients who discontinue early should return within 30 days of the last dose of the study drugs for a follow up evaluation. Any assessments listed for the final visit should be performed at that time.

In addition, any of the following conditions require withdrawal of the subject from study treatment:

- Disease progression defined by RECIST 1.1
- Severe, unexpected toxicities/side effects
- Lost to follow up or non-compliance with the protocol schedule
- An AE or current illness that in the opinion of the investigator or sponsor warrants the subject's withdrawal from treatment
- Necessary treatment with other investigational drug or other anticancer medications prohibited by protocol
- Participation in another clinical study using anti-cancer agents
- Request by regulatory agencies for termination of treatment of an individual subject or all subjects under this protocol
- Sexually active subjects who refuse to use medically accepted barrier methods of contraception during the course of the study and for 3 months following discontinuation of study treatment
- Women who are pregnant or are breast feeding
- If the patient withdraws consent for continued participation, he/she will be removed from study.

The reason for study treatment discontinuation will be documented. For subjects who discontinue or are withdrawn from study treatment, every effort must be made to undertake protocol specified follow up procedures and end of treatment assessments, if possible unless consent to participate in the study is also withdrawn.

If a subject is discontinued from study treatment because of an AE considered to be related to study treatment and the event is ongoing 30 days after the last dose of study treatment, the event

Columbia University Medical Center
Herbert Irving Comprehensive Cancer Center
Version Date: 27 Jul 2023

must be followed until resolution or determination by the investigator that the event has become stable or irreversible.

If a subject withdraws consent to participate in the study the reason for withdrawal will be documented, no further study procedures or assessments will be performed, and no further study data will be collected for this subject other than the determination of survival status from public records such as governmental vital statistics or obituaries.

Data Collection and Follow-up for Withdrawn Subjects

Even though subjects may be withdrawn prematurely from the study, it is imperative to collect at least survival data on such subjects throughout the protocol defined follow-up period for that subject (though careful thought should be given to the full data set that should to be collected on such subjects to fully support the analysis). Such data is important to the integrity of the final study analysis since early withdrawal could be related to the safety profile of the study drug. If a subject withdraws consent to participate in the study, attempts will be made to obtain consent from the subject to record at least survival data up to the protocol-described end of subject follow-up period. It must be a high priority to try to obtain at least survival data on all subjects lost to follow-up and to note what methods should be used before one can state the subject is truly lost to follow-up (e.g. number of phone calls to subject, phone calls to next-of-kin if possible, certified letters, etc.). Subjects withdrawn because of unacceptable adverse events will be followed-until resolution or stabilization of the adverse event.

